### **Biological Markers.**

Overview. Subjects will donate saliva and blood for genetic and biomarker research studies. Both saliva and blood will be collected because some biomarkers are known to be present in both blood and saliva. If we find a biomarker for PTSD symptoms in blood, and it is also in saliva, that would be a great advantage for monitoring. Also, there are species of proteins in saliva that are not carried in the blood, and which change with stress. These may also be biomarkers for PTSD symptoms. No clinically validated tests will be performed. The genetics/biomarker component of the protocol will be supervised by [name] (CoE Biomarkers and Genetics Core; Phase I, II, III), an expert in this area, in collaboration with the PI, [name]. See Appendix for Safety Survey. At the BL assessment, participants will be given the option of consenting to all study procedures or all procedures excluding the saliva/blood sample (depending on the phase) and genetic research.

Study participants will be donating their samples for biomarker and genetic-related studies. The samples (blood/saliva) will be collected from the study participants and will be analyzed for identifying molecular biomarkers for early diagnosis and prevention of traumatic brain injury and PTSD in our returning war Veterans. Genetic variation will also be studied between the patient vs. the control group of participants for predicting PTSD susceptibility and progression. The study participants will be donating their samples for the biomarker and genetics related studies. The process of biomarker identification and validation will be conducted in two stages 1) Unbiased approach (discovery) and 2) Targeted approach.

Stage I (unbiased approach): This is the discovery phase where samples will be analyzed globally to identify potential biomarkers (protein, genetic, epigenetic, metabolic, and immunological markers). Protein (proteomics) and metabolite (metabolomics) biomarkers will be screened with mass spectrometric analysis at the Mass Spectrometry Core facility, Baylor University, Waco, TX (under CTVHCS's MOU with Baylor). Genetic markers (allelic, mutations, CNV's, SNPs, miRNA) will be screened at the VA by using PCR, Real-Time Quantitative PCR, Droplet Digital PCR, and next-generation sequencing. Inflammation and immune biomarkers will be screened by flow cytometric analysis at the CoE Biomarkers & Genetics Core laboratory. If de-identified samples are sent outside the VA for analysis, we will follow all VA rules and regulations and obtain appropriate Research Service, IRB, safety and data monitoring approval.

Stage II (targeted approach): Once we narrow down the potential biomarkers, we will move to the qualification, verification, and validation steps where we will target the specific potential biomarker and proceed with a targeted screening approach. Once validated, the markers identified will be segregated according to susceptibility, diagnostic, and therapy biomarkers.

Sample Collection: Participants will donate saliva by passive drool, a method of pooling saliva in the mouth and pushing it through a straw or collection device into a collection tube. Staff will be trained to avert their eyes when participants are depositing saliva into the test tube to reduce potential embarrassment. Because many factors can influence salivary biomarkers, participants will complete a saliva questionnaire (included in Table 3 and appendices). The saliva samples will be stored in a cooler with an ice pack or in a refrigerator until transported to the Center of Excellence (Building 93), processed and stored until assay.

Subjects can also opt to donate blood by venipuncture by personnel trained in VA procedures for taking blood samples. All blood processing will take place at the VA by trained personnel. Compression bandages will be used to cover the puncture. Blood will be placed in 1 RNA (Paxgene Red-top), 1 DNA (Paxgene Blue-top), 2 purple top (plasma) and two red top (serum, activator coated), all coded, and stored in a cooler with an ice pack or refrigerator until transported to the Center of Excellence (Waco Building 93) within 4-6 hours of collection. If the participants have a fear of needles, blood will not be drawn in Phase III.

Tubes will either be frozen (RNA, DNA) or processed (redtop and purple top tubes) for cell protein and other constituents in Waco building 93 (2A113, 2A116, 2A117). DNA/RNA extraction from the DNA/RNA tubes will be performed by team members using DNA/RNA extraction kits and coded DNA/RNA samples will be stored at -20/-80 and in liquid nitrogen until testing. Blood will also be analyzed for immune and inflammatory markers (cluster of differentiation (CD) immunomarkers, chemokines, cytokines), as well as for other blood and saliva-based biomarkers. Remaining blood product samples will be stored at -20/-80°C and in liquid nitrogen for future use, with appropriate IRB approval at CoE (Freezer Room 2A13). DNA genotyping and lab work will be performed in the wet lab within the CoE (Waco building 93; room 2A113, 2A116, 2A117). The results of any biomarker analysis will be saved in a coded, de-identified dataset and stored on VA computers on the secure CTVHCS Research Service-approved drives that will only be accessible to study staff.

**Data Management:**

Identifiers: A study ID number will be used to identify each participant across assessments.

Identifiers/linking data: A password protected master participant tracking spreadsheet will contain the linking information that matches the participant IDs to participant names. This spreadsheet will reside only on the secure research drive. Other PHI such as participant addresses and phone numbers (for follow-up contact), and date of participation will only be accessible to PI [name] and her research staff that is approved to work on the study. The Master tracker will be kept separately from study databases on the secure research drive. Paper files will be stored at the VISN 17 Center of Excellence in Waco, TX in Building 93, room 1A-137.

Confidentiality: No participant will be identified in any publications or presentations arising from this study. Records will be maintained in accordance with the Department of Veterans Affairs Record Control Schedule 10-1. It may be necessary or required for the study investigators to break confidentiality and release personal identifiers and health information when mandated by law. For example, state law requires health care workers to report any suspected abuse or neglect of a child, or person 65 years or older, or an adult with disabilities to the Texas Department of Family and Protective Services.

A Certificate of Confidentiality will be obtained from the National Institutes of Health prior to the commencement of research. The purpose of this certificate is to protect the identity of research subjects participating in studies that collect sensitive information. No information about participants will be released without their permission or where required by law (such as the examples given above).

All employees who are to handle data will be trained in confidentiality policies and procedures. If theft, loss, or other unauthorized access of sensitive data and non-compliance with security controls occur, study staff has been instructed to follow the CTVHCS standard operating procedure on incidence reporting.

Delineation of research tasks performed by VA and collaborators: All participant contact activities will take place on the Austin, Temple or Waco campuses of CTVHCS. Following approved CTVHCS methods for sharing a study dataset with collaborators, some secondary outcomes analyses may be performed by approved secondary users within and outside the VA through requests made to the SERVE Data Repository.

Primary users of the study dataset are those individuals listed on the study staff list and are those who will conduct pre-specified analyses consistent with the study's hypotheses and its primary, secondary and exploratory aims as described in the aims and analysis plan.

Disposition of the data: Paper files containing identifiers will be kept in locked file cabinets in a locked room at the Center of Excellence in Waco, TX. Coded paper files will be kept in separate locked file cabinets. Only approved study staff will have access to the files. Electronic data will be stored on the secure VA password-protected server with access restricted to research staff. These records will be maintained and retained in accordance with the Department of Veterans Affairs Record Control Schedule 10-1.

Incident Reporting: Any incidents affecting the security of the data such as theft, loss, or unauthorized access of sensitive data will be reported to the ISO and PO per VA regulations.

Data Use within CTVHCS: Only IRB approved personnel on the study staff list will have access to the data

collected in this study. Access to the study data will be terminated when personnel are no longer part of the research team. The primary repository of paper files generated by the study is the VHA VISN 17 CoE. Data to be transported to the CoE includes: consent documents and measures completed after each appointment. Study data collected at the Temple or Austin campus will be transported to the approved data storage location at the Waco Campus where it will be uploaded to the secure research drive. Personally-identifying information (e.g. Informed Consent Form with name and date of consent) will be kept in a separate locked carrying case from the data during transport.

Records destruction information: "All paper AND electronic documentation containing confidential, personally identifiable information, protected health information, and any other sensitive information will be disposed/destroyed per current VA regulations at the time of disposal/destruction of documentation."

Records retention information: "The required records, including the investigator's research records, must be retained until disposition instructions are approved by the National Archives and Records Administration and are published in VHA's Records Control Schedule (RCS 10-1)." All de-identified data will be managed in accordance with the VHA Handbook 1605.1 APPENDIX B. All original data will be stored at VA.

Reporting: Any incidents involving theft or loss of data or storage media, unauthorized access of sensitive data or storage devices or non-compliance with security controls will be immediately reported to the IRB chair, Privacy Officer and Information Security Officer.

Data Analysis Software: Data will be analyzed using the software programs that are already owned by the VA (e.g., SPSS, SAS, mPLUS, AMOS) either using local copies of the software or through VA Informatics and Computing Infrastructure (VINCI).

**Data Collection.** Data will be visually inspected for completeness by study interviewers at the time of collection. Data will be gathered in two ways: collected and entered using hard-copy assessment measures or through the use of Qualtrics, a secure web-based survey application. Qualtrics is a secure, web-based application for building and managing online surveys and databases. This system is similar to REDCap and is flexible enough to be used for a variety of types of research, and provides an intuitive interface for participants to complete surveys. It also offers easy data manipulations with audit trails for reporting, monitoring, and querying patient records, and an automated export mechanism to common statistical packages. As with REDCap, all web-based information transmission is encrypted. Data from Project SERVE: FX (00390) will be stored on VA servers, including data downloaded/exported from Qualtrics. Data will be entered and managed using statistical software (SPSS, SAS, Stata, R/S-Plus, and others) and through Research Electronic Data Capture (REDCap). REDCap is a service through the VA Information Resource Center (VIREC; for more information, please see: <http://vaww.virec.research.va.gov/REDCap/Overview.htm>). REDCap is a secure, web-based application for building and managing online surveys and databases. REDCap data collection projects rely on a thorough study-specific data dictionary defined in an iterative self-documenting process by all members of the research team. The iterative development and testing process results in a well-planned data collection strategy for individual studies. The REDCap system provides secure, web-based applications that are flexible enough to be used for a variety of types of research, provide an intuitive interface for users to enter data and have real time validation rules (with automated data type and range checks) at the time of entry. These systems offer easy data manipulation with audit trails for reporting, monitoring and querying patient records, and an automated export mechanism to common statistical packages (SPSS, SAS, Stata, R/S-Plus). REDCap servers are housed in the secure, VA Information Technology Center on a VINCI server, located in Austin, TX. All web-based information transmission is encrypted. REDCap was developed specifically around HIPAA-Security guidelines. REDCap has been disseminated for use locally at other institutions and currently supports 240+ academic/non-profit consortium partners on six continents and over 26,000 research end-users ([www.project-redcap.org](http://www.project-redcap.org)). Interview and self-report data will be entered continuously by staff members as the data are collected. Data entry training will consist of both didactic sessions in which staff members are provided with information about the data entry system in place at the CoE as well as actual entry of mock data as a validity and accuracy check.

**Data Sharing With Other Studies Comprising Project SERVE.** Project SERVE: FX is one of several studies that will comprise the Project SERVE research program. Each study aims to independently contribute to scientific understanding of the impact of warzone experiences on OEF/OIF/OND Veterans. A data sharing agreement is requested between Project SERVE studies and a SERVE Data Repository has been established for future research. Data from Project SERVE will be included in the SERVE Data Repository.

## **AIMS AND HYPOTHESES.**

**Specific Aim 1: Identify treatment targets that prospectively predict functional disability and self-directed violence (SDV) in post-9/11 Veterans with PTSD, depression, chronic pain, TBI, and/or AUD.**

Hypothesis 1: Novel factors (mindfulness, perceived burdensomeness, thwarted belongingness, and moral injury) along with established treatment targets (psychological flexibility, self-compassion, and emotion regulation) will prospectively predict functional disability and SDV after accounting for covariates.

## **Analytical Plan.**

**Aim 1:** The proposed analyses are grounded in the SERVE conceptual framework (Figure H1a). Our team has expertise in a variety of advanced statistical modeling procedures, including latent growth models, growth mixture models, longitudinal analyses, and measurement invariance. The design is based on a measurement model that collects predetermined, repeated assessments every 8 months over a two-year period. The effect of treatment will be examined via dummy variables in all hypotheses. We will use both traditional (e.g., maximum-likelihood regression) and advanced approaches (e.g., latent growth models, growth mixture models, and mediation models with bias-corrected bootstrap confidence intervals) to analyze the data. For example, to test Hypothesis 1a (H1a) in a traditional manner, principal component analysis (PCA) will be used to create a composite functional impairment factor. This approach will greatly reduce the number of tests conducted and provide us with a broad index of functional impairment. Variables used to create this factor score will include measures of functional impairment (WHODAS 2.0, IPF), QoL (QLS), and values-based behavior (VT). Change scores for these measures will be calculated and regressed onto the hypothesized predictors and covariates (including prior level of functional impairment) to test H1a. Latent growth modeling (LGM)—which allows for modeling of the change/growth trajectory of different variables assessed on multiple occasions across time—will also be used to analyze the data. We expect that scores on repeated measures will be correlated. Growth models take this dependency into account by treating repeated measures as separate variables, and fitting a proposed trajectory shape to the scores across time. Advantages of using LGM over other approaches include the flexibility of placing constraints on the model while allowing growth parameters describing participants' trajectories to serve as predictors or outcomes. LGM assumes that individuals come from a homogeneous population while Growth Mixture Modeling (GMM) allows multiple subpopulations to be inferred from the data. GMM is a general latent class analytical framework that has the capacity to model both random variation of the latent growth factors and the unknown heterogeneous subpopulations simultaneously. The proposed mediation effects will be examined with bias-corrected bootstrap confidence intervals that have been shown to produce the unbiased test with highest statistical power. We will ensure adequate data quality by evaluating normality and conducting descriptive, outlier, and psychometric analyses for each data wave. We will use alternative robust estimators (e.g., WLSM, WLSMV, MLM, and MLMV) when analyzing non-normal data. All SEMs including the LGM and mediation analyses will be evaluated with the chi-square test and commonly used fit indices such as RMSEA, SRMR, CFI and TLI. Additionally, for GMM, we will evaluate the results using the recommended information criteria (e.g., BIC, BLRT) and other related fit statistics (e.g., entropy). Analyses will be registered in the NIH clinical trials online database prior to data collection.

The statistical power of the hypothesized models was estimated using the Monte Carlo procedure in Mplus. For each power analysis, 1000 datasets were simulated following a hypothesized model that included a particular effect size of interest for each test. The model(s) of interest were then estimated for each dataset, and the proportion of datasets in which the null hypothesis was rejected was taken as the (empirical) power of the test. To examine the effect of the novel and established treatment targets on functional impairment over time in Hypothesis 1a, we will use LGM with the treatment targets measured at baseline predicting functioning

over time (Figure H1a). The statistical power of the target effect, the direct arrow from the treatment targets to the slope of functional impairment over time, is evaluated. Given the proposed sample size (500 participants with 4 repeated measures), the power for detecting a medium direct effect (based on our preliminary analyses) from the treatment targets to the slope of functional impairment is  $> .90$ . GMM will be used to test Hypothesis 1b (Figure H1b). Based on our preliminary studies, the statistical power for detecting a three-class solution is larger than .90 given the proposed sample size (500 participants). We calculated statistical power for the effects of the novel and established treatment targets on latent class membership. Assuming a small to medium effect size (odds-ratio = 1.82, which roughly corresponds to Cohen's  $d$  of 0.34), the power of the treatment targets on predicting class membership ranged from .72 to .91. In Hypothesis 1c, risk for SDV is measured in multiple ways including a continuous variable (severity of suicidal thoughts), a frequency/count variable (number of instances of NSSI), and a dichotomous variable (attempted suicide). A latent factor will be created and analyzed in Mplus which uses the MLR estimation to handle non-normally distributed variables. The longitudinal property of this latent factor will be examined via the longitudinal measurement invariance. Once the risk for SDV factor model is confirmed, we will regress it on the latent class membership (based on H1b results), hypothesizing that the most severely impaired class will predict greater risk of SDV. The proposed mediation model in Hypothesis 1d (i.e., the treatment targets mediate the effects of mental and physical wounds on functional impairment and risk for SDV over time) will be tested by using Mplus MODEL INDIRECT with bootstrap confidence intervals. By assuming a medium mediation effect, the corresponding statistical power is larger than .80 with our proposed sample size. We used conditions and parameters that are broadly based on our own data, prior clinical studies, and published Monte Carlo studies. Effect sizes estimates were in the small-to-medium range. The number of repeated measures is based on the current design. In brief, we are confident that the parameters and conditions are very close to our proposed study conditions.

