### **Aims and Hypotheses**

**Specific Aim 1:** Identify clinically-relevant, modifiable psychosocial factors that predict improved functioning over time.

*Hypothesis 1a:* Higher levels of acceptance, self-compassion, and positive attributions, and better emotion regulation will predict improved functioning over time after accounting for the covariates (number of TBI exposures, combat exposure, time since deployment, physical health symptoms).

**Specific Aim 2:** Identify clinically-relevant, modifiable psychosocial factors that predict membership in latent class trajectories of functioning.

*Hypothesis 2a:* Higher levels of acceptance, self-compassion, and positive attributions, and better emotion regulation will predict membership in the least impaired trajectory after accounting for the covariates.

*Hypothesis 2b:* Lower levels of acceptance and self-compassion, and greater negative attributions and emotion dysregulation will predict membership in the most impaired trajectory after accounting for the covariates.

**Specific Aim 3:** Identify clinically-relevant, modifiable psychosocial predictors of transitions between trajectories of functioning.

*Hypothesis 3a:* Higher levels of acceptance, positive attributions, self-compassion, and emotion regulation will predict recovery (i.e., moving to a less impaired trajectory) after accounting for the covariates.

*Hypothesis 3b:* Lower acceptance and self-compassion and higher levels of negative attributions and emotion dysregulation will predict chronicity (i.e., staying on an impaired trajectory) after accounting for the covariates.

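### H1c and H1d sit under an aim of prospectively predicting self-directed violence, but no baseline self-directed-violence term is stated and the 24-month outcome is left to inference

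*Combined protocol and SAP*

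**What the plan says.** **The aim.** Under Aims and Hypotheses, Specific Aim 1 is to "Identify treatment targets that prospectively predict functional disability and self-directed violence (SDV") in post-9/11 Veterans. Hypothesis 1 says that the novel and established targets "will prospectively predict functional disability and SDV after accounting for covariates". The section does not say what the Phase III covariates are. The completed Phase II section does list its own: "after accounting for the covariates (number of TBI exposures, combat exposure, time since deployment, physical health symptoms").

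**H1c.** The Analytical Plan forms a latent SDV factor from a continuous measure (suicidal thoughts), a count (NSSI) and a binary measure (attempt). "The longitudinal property of this latent factor will be examined via the longitudinal measurement invariance". Then "we will regress it on the latent class membership (based on H1b results), hypothesizing that the most severely impaired class will predict greater risk" (the risk meant is SDV). No outcome wave and no earlier SDV level are given.

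**H1d.** The mediation hypothesis is that "the treatment targets mediate the effects of mental and physical wounds on functional impairment and risk for SDV over time". Again there is no wave and no prior-SDV term.

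**Adjustment that is stated.** For the H1a change-score regression, the predictors are accompanied by "covariates (including prior level of functional impairment) to test H1a". For every hypothesis, "The effect of treatment will be examined via dummy variables in all hypotheses".

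**Schedule.** In Table 1 (Phase III instruments), the Columbia scale, the CANDI and the BSSI are ticked at baseline and 24 months only. PHQ-9, which has a suicidal-ideation item, is ticked at every wave. The Analytical Plan does not say which instruments feed the SDV factor.

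**The concern.** More impaired Veterans may already carry more SDV risk at entry, and SDV risk tends to persist. If so, class or target will be associated with 24-month SDV even when it says nothing about later SDV beyond what was known at baseline. A model without baseline SDV cannot separate that from genuine prediction of later risk.

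The plan names prior level where the outcome is functional impairment (H1a) and gives no parallel term where the outcome is SDV. The invariance step implies that more than one SDV wave is modelled, so an adjusted model is possible. But invariance concerns measurement; it does not condition one wave on another. The treatment dummies do not stand in for baseline SDV either.

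At stake is what a positive H1c or H1d may be called. The aim's wording is prospective; a baseline association carried forward would be a weaker finding.

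**Working it through.** The plan states no power or effect size for H1c, so there is no figure to reproduce. The check asks how often an unadjusted H1c test is positive when class adds nothing beyond baseline SDV.

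**Inputs from the documents.** N = 500; four waves (0, 8, 16, 24 months); likely SDV instruments at baseline and 24 months.

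**Assumed inputs (not in the documents).**
- Class shares 40/35/25%; functioning intercepts 0/1.5/3.0; 24-month slopes 0/0/0.3; within-class SDs 0.60 (intercept), 0.40 (slope), 0.80 (residual).
- Modal worst class compared with the rest.
- Baseline SDV (SDV0) correlates r with baseline functioning.
- SDV24 = a × SDV0 + noise, SD 1, stability a = 0.3 or 0.5.
- Continuous SDV score; no other covariates; two-sided 5% test.

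**Hand calculation.** With worst-class share q = 0.25 and standardised worst-versus-rest difference d at 24 months,

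rejection ≈ Φ(d√(Nq(1−q)) − 1.96) + Φ(−d√(Nq(1−q)) − 1.96),

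where √(500 × 0.25 × 0.75) = 9.68.

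At a = 0.5, the simulated d is 0.15/0.22/0.30 for r = 0.2/0.3/0.4. Then d × 9.68 = 1.45/2.13/2.90, which gives 31%/57%/83%. For r = 0.1, halving 0.15 gives 0.075, and 0.075 × 9.68 = 0.73 gives 11%. At a = 0.3 each d is multiplied by 0.6 (0.3/0.5): 0.045/0.09/0.132/0.18 gives 7%/14%/25%/41%.

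**Simulation, same structure.**

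| r | a = 0.3, unadjusted | a = 0.5, unadjusted | baseline SDV in model |
|---|---|---|---|
| 0.1 | 7% | 13% | about 5% |
| 0.2 | 16% | 30% | about 5% |
| 0.3 | 28% | 63% | about 5% |
| 0.4 | 45% | 86% | about 5% |

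**How far this depends on the set-up.**
- *Latent factor* with continuous, count and binary indicators, a = 0.5, r = 0.2/0.3/0.4: 27%/50%/75% unadjusted; 5%/5%/3% with the baseline factor.
- *Truncated baseline SDV* (the crisis-risk exclusion mimicked by removing the top 10%) plus 20% missing at 24 months: 14%/30%/46% unadjusted; 4-6% adjusted.
- *One covariate* correlated 0.3/0.4/0.5 with both baseline functioning and baseline SDV, at r = 0.3 and a = 0.5: about 63% falls to 38%/19%/6%. The reduction is not universal: at r = 0.1, a covariate correlated 0.5 with both gave 24%.
- *H1d* indirect effect (bias-corrected bootstrap, a = 0.5, partial target-to-baseline-SDV path 0.1/0.2/0.3): 19%/57%/89% unadjusted; 5-7% with baseline SDV.
- *Shared visit.* If the classes use the 24-month wave and functioning and SDV have a same-visit link of 0.2/0.3, the baseline-adjusted test rejects 8%/14%. With classes from months 0 to 16 it rejects 5%/6%.

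**The case against.** **The covariates may include baseline SDV.** They are unlisted, not absent, and nothing rules it out. This stands. A reader might take the unadjusted percentages as the error rate of the plan as written. The documents do not support that: the illustration carries no covariates or treatment terms, and one moderately correlated covariate can remove most of the excess.

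**The outcome wave is not really open.** The likely instruments have only one follow-up tick, and the aim says prospective, so 24 months is the natural reading. This largely stands. What remains is that the analysis text does not commit to it.

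**H1c may be a marginal hypothesis.** Its stated prediction is only that the worst class carries greater SDV risk. For that claim the percentages are power to detect a real difference. This stands, and it is why labelling matters. Trajectory class is also not a treatment target, so even an adjusted H1c would not by itself support the choice of a target.

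**Baseline adjustment in H1d is partly a choice of estimand.** Long-standing wounds and targets may already have affected SDV by entry, and conditioning on baseline SDV removes that part of the pathway. This stands and argues for reporting both versions.

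**Figures H1a and H1b are not shown.** The text ties them to H1a (and the overall framework) and to H1b; it cites no figure for H1c or H1d. The H1a regression is introduced as an example, so the lack of a parallel term is weak evidence of intent. That limits confidence but does not supply the missing term.

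**Conclusion.** The point holds in a limited form. The aim is prospective, and the plan states neither a baseline-SDV term for H1c or H1d nor the Phase III covariates. If baseline SDV is left out, a positive result can come from baseline association plus persistence alone.

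The illustration fixes direction more than size: about 7-13% at r = 0.1 and 45-86% at r = 0.4, against about 5% with adjustment. It rests on assumed correlation, stability and class structure, a continuous score and no other covariates. The rates are errors only for a claim that class adds to baseline SDV.

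A reader might infer that the plan excludes baseline SDV, or that H1c is bound to mislead; the text supports neither. This is worth fixing, with medium confidence, because baseline adjustment may have been intended. The shared 24-month visit is secondary and conditional: that the H1b classes use all four waves is inferred from the H1a power statement.

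**What to change.** 1. **H1c:** name the 24-month SDV factor as the outcome and include the baseline SDV factor as a covariate. List the Phase III covariates.
2. **H1d:** report the SDV indirect effect with and without baseline SDV. Note that the adjusted version targets change since baseline and may remove effects already present then.
3. **Labelling:** call any unadjusted result an association, not prospective prediction.
4. **If the H1b classes use the 24-month wave:** add a sensitivity analysis with classes from months 0, 8 and 16.

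**Cost.** Plan wording only, provided the SDV factor uses the instruments already scheduled at baseline and 24 months. The adjusted test has less power: in the latent-factor illustration (200 replicates), about 57% for a true 0.3 SD class effect beyond baseline, with the estimate shrunk to about 0.24 by modal class assignment. A null adjusted result should therefore not be read as no effect. Three-wave classes separate slightly less well (modal accuracy 0.755 against 0.772 with four waves), and some overlap remains if the NSSI or attempt recall window reaches back before month 16.
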